### **Serious Adverse Event or Serious Adverse Reaction**

An SAE or Serious Adverse Reaction (SAR) is defined as any untoward medical occurrence or effect that at any dose:

- Results in death
- Is life-threatening\*
- Requires inpatient hospitalisation\*\* or prolongation of existing hospitalisation
- Results in persistent or significant disability or incapacity
- Is a congenital anomaly/birth defect

For cancer trials we would also include:

- New primary cancer

#### ***Comment***

Medical judgment should be exercised in deciding whether an AE or AR is serious in other situations. An AE or AR that is not immediately life threatening or does not result in death or hospitalisation but may jeopardise the subject or may require intervention to prevent one of the other outcomes listed in the definition above, should be considered serious.

\*Life threatening in the definition of an SAE or SAR refers to an event in which the patient was at risk of death at the time of the event; it does not refer to an event that hypothetically might have caused death if it were more severe.

\*\*Hospitalisation is defined as an inpatient admission, regardless of length of stay, even if the hospitalisation is a precautionary measure for continued observation.

### **Suspected Unexpected Serious Adverse Reactions**

A Suspected Unexpected Serious Adverse Reaction (SUSAR) is defined as a SAR that is unexpected i.e. the nature, or severity of the event is not consistent with the applicable product information.

A SUSAR should meet the definition of an AR, UAR and SAR as detailed above.

### **13.2 Procedures for collecting Adverse Events**

All medical occurrences (which meet any of the above definitions) from the first dose of IMP to 30 days after the last dose of IMP should be reported as adverse events and must be accurately recorded on the appropriate trial CRF and sent to the NEO-EXCEL Study Office.

Toxicities will be reviewed using the National Cancer Institute Common Toxicity Criteria (NCI CTC version 3.0, see Appendix 5). Any toxicities incurred but not categorised by the NCI CTC should be graded by the physician and be recorded on the CRF using a scale of (1) mild, (2) moderate or (3) severe (as defined in Appendix 6). For each sign/symptom, the highest grade observed since the last visit should be recorded.

## Exceptions to AE reporting

- A pre-existing condition should not be reported as an adverse event unless the condition worsens or episodes increase in frequency during the adverse event-reporting period
- Symptoms of the targeted cancer should not be reported as adverse events
- Symptoms relating to disease progression or death unless the investigator deems them related to use of the study drug
- Symptoms related to treatment for disease progression

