### At Screening

- Relevant medical history including:
  - cardiac history
  - thromboembolic history
  - rheumatological history
  - other serious acute or chronic conditions
- Concomitant medication (description of other medication prescribed for more than 7 days and taken within one month of randomisation)
- ECOG performance status (Appendix 1)
- Clinical examination, including height and body weight
- Uni-dimensional tumour measurement by calipers of the greatest dimension
- Tumour assessment by ultrasound
- Base-line blood tests: full blood count; urea + creatinine + electrolytes; liver function tests
- Blood pressure measurement
- NYHA classification (see section 6.2)

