### At Baseline

- Clinical examination
- Core biopsy - if insufficient material left from diagnostic core biopsy. (See separate Pathology Consent Form. If this Consent Form is used before diagnostic biopsy and sufficient cores taken, other additional biopsies will not be necessary at baseline).
- Frozen core biopsy (**only for sites participating in the frozen tissue sub-protocol**)
- Trans NEO-EXCEL bloods (pre-treatment)

### At Day 14

- Treatment side-effects
- Core biopsy
- Frozen core biopsy (**only for sites participating in the frozen tissue sub-protocol**)
- Trans NEO-EXCEL bloods

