## FIGURE 1: FLOWCHART OF ASSESSMENTS

This table provides a summary of the trial-related procedures required; refer also to full text in section 9

YEAR	1						FOLLOW-UP
	S 	B 	2	3	4	5	
Visit							
Timeframe		Day 1	Day 14	4 wks	8 wks	12 wks	16 wks
Medical history	X						
Clinical examination	X	X		X	X	X	X
Events 				X	X	X	X
Adverse Events/SAEs 			X	X	X	X	X
Tumour assessment by calipers	X			X	X	X	X
Tumour assessment by ultrasound	X						X
Routine bloods	X						X
Trans NEO-EXCEL Bloods		X	X				X
Core Biopsy		X	X				
Formalin fixed tumour tissue cut from surgical specimen							X*

FROZEN TISSUE SUB-PROTOCOL Frozen core biopsies** and frozen sample from* surgical specimen		X**	X**				X*	
--	--	-----	-----	--	--	--	----	--

The Trans NEO-EXCEL sub-protocol is applicable to all sites

The frozen tissue sub-protocol will only apply to sites that are participating in frozen tissue collection

If for any reason Trans NEO-EXCEL blood samples cannot be taken always send all pathology samples

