**Refer to Investigator Site File/Pharmacy File for procedure outwith office hours.**

## 14. STATISTICAL CONSIDERATIONS

### 14.1 Definition of Outcome Measures

The treatment arms will be compared in terms of the following outcome measures:

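### The protocol schedules no pre-treatment grade of subjective symptoms, so the rule that a pre-existing condition is an adverse event only if it worsens has no recorded graded reference

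*Protocol*

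**What the plan says.** - **Rule (section 13.2, among the exceptions):** "A pre-existing condition should not be reported as an adverse event unless the condition worsens or episodes increase in frequency".
- **Window (section 13.2):** medical occurrences "from the first dose of IMP to 30 days after the last dose of IMP should be reported as adverse events".
- **Grading (section 13.2):** NCI CTC version 3.0. "For each sign/symptom, the highest grade observed since the last visit should be recorded". A pre-treatment grade is not mentioned.
- **Screening (section 9):** cardiac, thromboembolic and rheumatological history, then "other serious acute or chronic conditions". Concomitant medication, ECOG status, examination, blood tests, blood pressure and NYHA class are also recorded. No symptom is graded.
- **Baseline (section 9):** examination, biopsies and translational blood samples. The item "Treatment side-effects" first appears in the day 14 list.
- **Figure 1:** the row "Adverse Events/SAEs" is blank at screening and baseline. It is marked at day 14 and then at the four-weekly visits.
- **Use of the data (sections 10.8 and 14.4):** interim analyses cover toxicity and adverse events, and the IDMC may consider stopping the trial for excessive toxicity.

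**The concern.** To say that a symptom has worsened, one needs to know how bad it was before the first dose. For laboratory values and blood pressure the protocol records that. For subjective symptoms it does not, and the history taken at screening is ungraded and, outside the three named areas, limited to serious conditions. Non-serious hot flushes or dyspepsia need not be recorded at all. The introduction to section 9 also lets information stay in the patient notes where the CRF does not require it.

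The symptoms affected are ones the protocol itself expects: hot flushes and joint pain with aromatase inhibitors, and diarrhoea with exemestane. Postmenopausal women can have them before treatment. Section 8.2 has HRT stopped when trial treatment starts, so menopausal symptoms may change in any arm for a reason unrelated to the study drugs, with no earlier grade to set the change against.

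Sites are left to report symptoms that were already there, or to leave out symptoms from memory. No analysis plan can recover a grade that was never collected.

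**Working it through.** The protocol gives no sample size, power or error rate for toxicity, so there is no stated figure to reproduce. The prevalences and toxicity rates below are assumptions. Only the 500 v 500 margin comes from the protocol (section 14.3).

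**Model.** Let b be the share of patients with the symptom before treatment and r the rate of new symptoms among the others. If every pre-existing symptom is counted, the reported rate is b + (1 − b)r. If none is counted, even when it has worsened, it is (1 − b)r.

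**Absolute rates.** With b = 25% and r = 10%:
- all counted: 0.25 + 0.75 × 0.10 = 32.5%
- none counted: 0.75 × 0.10 = 7.5%

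The reported rate can fall anywhere between these, depending on how sites apply the rule.

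**Dilution.** Take r = 10% v 16%, two-sided 5%, and power = Φ[(d − 1.96·SE₀)/SE₁], where d is the difference, SE₀ its pooled and SE₁ its unpooled standard error. For b = 25% the rates are 32.5% and 0.25 + 0.75 × 0.16 = 37.0%, so d = 0.045, SE₀ = 0.0301 and SE₁ = 0.0301. Power = Φ[(0.045 − 0.0590)/0.0301] = 32%. The last column compares only the 500(1 − b) patients per group without the symptom at baseline.

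| b | Rates, all counted | Difference | Power, all counted | Power, symptom-free at baseline |
|---|---|---|---|---|
| 10% | 19.0% v 24.4% | 5.4 points | 54% | 76% |
| 25% | 32.5% v 37.0% | 4.5 points | 32% | 69% |
| 40% | 46.0% v 49.6% | 3.6 points | 21% | 59% |

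A second pair of rates behaves the same way. For 5% v 10%, power is 85% with no prior symptoms counted (b = 0), 48% at b = 10%, 30% at b = 20% and 16% at b = 40%.

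**Bias when miscounting is equal in the arms.** With a true rate of 10% in both arms, 200,000 simulated trials rejected in 5.0% (b = 0), 5.0% (b = 20%) and 5.3% (b = 40%). Equal miscounting does not create a false difference of any note.

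**Bias when miscounting is unequal.** This is possible where the assessor knows the drug. Assume b = 25%, r = 10% in both arms, and 40% v 60% of prior symptoms reported. The rates are 0.075 + 0.25 × 0.40 = 17.5% and 0.075 + 0.25 × 0.60 = 22.5%. With SE₀ = 0.0253 and SE₁ = 0.0252, the chance of a significant result is Φ[(0.05 − 0.0496)/0.0252] = 51%, although the drugs do not differ.

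**The case against.** A reader might infer that the toxicity comparison cannot separate drug effects from symptoms already present. The protocol does not support that. Allocation is randomised 1:1:1:1 and celecoxib is compared with placebo capsules, so prior symptoms are balanced in expectation. The inference is true of a single patient and of an absolute rate, not of the randomised contrast.

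A reader might also infer that nothing is captured before day 14. That is wrong: reporting opens at the first dose, and day 14 is only the first scheduled visit at which side-effects are asked about. Still, this supplies no pre-dose grade.

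Third, pre-treatment information is not absent. Blood tests, blood pressure, NYHA class and a rheumatological history are taken, and active peptic ulcer, inflammatory bowel disease and a regular NSAID requirement are exclusions. This narrows the gap to subjective symptoms but does not close it.

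Fourth, the On-study Form listed in section 10.2 might collect baseline symptoms. Its content is not shown. What can be said is that the protocol text does not require it.

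Fifth, the all-counted figures assume that sites ignore the exception in 13.2 completely, so they are an upper bound. The symptom-free comparator is not the proposed remedy either, so the gap between the two power columns does not measure what the fix would gain. Both points stand.

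Finally, toxicity is not in the section 14.1 list introduced by "The treatment arms will be compared in terms of the following outcome measures", and one might call that an omission. It is not a fault here: toxicity comparisons and their analysis population are commonly left to the statistical analysis plan.

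**Conclusion.** The point holds in a limited form. The protocol makes a before-and-after judgement decide what is an adverse event, but schedules no graded reference for subjective symptoms. Three consequences follow:

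- Absolute toxicity rates, including those the IDMC sees, may be too high or too low.
- The placebo-controlled celecoxib comparison loses sensitivity but is not biased.
- The open-label exemestane v letrozole comparison is exposed to recall and to unblinded judgement of what is worse.

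The size is unknown. At worst, under the assumed prevalences of 10% to 40%, a 6-point difference in new symptoms (10% v 16%) shrinks to between 5.4 and 3.6 points. The real loss should be smaller to the extent that sites apply the exception. The 51% figure for unequal reporting shows what could happen under its assumptions and is not a forecast. No primary or secondary outcome is affected. This is a cheap improvement to data collection that cannot be made retrospectively.

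**What to change.** In section 9 and Figure 1, add CTCAE v3.0 grading of the expected symptoms (hot flushes, joint pain, gastrointestinal symptoms) to the baseline visit, before the first dose. In 13.2, define worsening as a grade above that baseline, and keep the existing criterion of increased frequency.

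The cost is one extra CRF page at a visit that already takes place, with no new procedure. A recorded baseline grade reduces the discretion in the open-label comparison but does not remove it, because the later grade is still assigned by someone who knows the drug.

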### 13.3 Recording and reporting Serious Adverse Events

In the case of a SAE the Investigator (or person delegated that responsibility) must **immediately** on becoming aware of the event:

- **Complete a ‘Serious Adverse Event Form’.** This should contain all of the information known at the time of the report
- **Fax** within 24 hours of becoming aware of the event the signed and dated ‘Serious Adverse Event Form’ to the NEO-EXCEL Study Office at the CRCTU, Birmingham: **UK [contact] or [name]**
- In addition, **send by post** the original copy of the SAE form and ensure that the reporting clinician has signed/dated it. Forms can be signed by nurse but must be co-signed by the reporting Investigator.

Investigators should also report SAEs in accordance with their local institutional policy.

#### Documenting SAEs

The responsible clinician must determine the severity of an event (according to the NCI CTCAE-3, see Appendix 5), and relatedness of the events to the study drugs. Seriousness, relatedness, and expectedness will also be independently assessed by the Clinical Coordinator(s). A SAE judged by the Investigator or Clinical Coordinator to have a reasonable causal relationship with the trial medication will be regarded as a Serious Adverse Reaction (SAR). If the event meets the definition of a Serious Adverse Reaction that is unexpected in nature it will be classified as a Suspected Unexpected Serious Adverse Reaction (SUSAR).

#### Reporting period for SAEs

Details of all SAEs will be documented from the commencement of treatment until 30 days post-treatment (i.e. 30 days from last administration of the study drug). SAEs occurring thereafter should be reported only if the Investigator believes them to be related and unexpected (i.e. SUSAR).

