### **Warfarin**

Because of possible interference with INR and also due to multiple biopsies being required, patients on warfarin are ineligible. Tumour measurements may also be affected by excessive bleeding.

Caution is advised when patients are receiving drugs with a narrow therapeutic index and which are mainly dependant on cytochrome CYP 450 enzymes 2A6 and 2C19.

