#### 13.1 Adverse Event definitions

##### **Adverse Event**

An Adverse Event (AE) is defined as any untoward medical occurrence in a patient or clinical trial subject administered a medicinal product and which does not necessarily have a causal relationship with this treatment.

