### Fixed tissue bank and serum bank

All 1000 patients randomised into the NEO-EXCEL trial will have primary core biopsies (taken prior to treatment) in order to provide material for diagnosis. Additional core biopsies will be taken for formalin fixation to provide material for the TRANS NEO-EXCEL research tissue bank. This will ensure that sufficient tissues, since core biopsies are not suitable for modifying into a tissue micro-array, will be available to test the hypotheses outlined below and those which may arise from the expression profiling described above.

In addition, we will retrieve tumour resection specimens to construct a tissue microarray in which to evaluate markers of clinical response identified by tissue expression profiling. Tissue will be collected at the central research laboratory (Endocrine Cancer Group) where material will be sectioned for further study/made into tissue microarrays.

The key hypothesis to be tested prospectively within TRANS NEO-EXCEL relates to the observed interaction between COX 2 and aromatase expression as a model to explain the efficacy of COX 2 inhibitors, such as celecoxib, in the treatment of invasive breast cancer. The product of the COX 2 enzyme, PGE2, induces expression of the transcription factors Snail/Slug which co-operatively modulate the I.3 promoter region of the aromatase gene. Paradoxically Snail/Slug are also closely involved in the regulation of E-Cadherin expression. Loss of E-Cadherin has been associated with increased tumour metastatic potential. Using paired pre/post treatment samples from TRANS NEO-EXCEL we will test the hypothesis that reduction of PGE2 production in breast cancer, via celecoxib treatment, reduces the metastatic potential by up-regulation of E-Cadherin expression. We will further test the hypothesis that down-regulation of Snail/Slug expression is linked both to alterations in E-Cadherin expression and to a reduction in aromatase expression (each of these markers will be measured by immunohistochemistry). There has been significant recent progress towards the identification of an appropriate antibody for aromatase analysis in paraffin embedded tissues (presented at the AROMATASE 2004 meeting in Edinburgh). We recognise however that this latter hypothesis may be also influenced

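### AE and SAE collection opens at the first dose, so a complication confined to the days between a pre-treatment research biopsy and that dose has no trial reporting route

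*Protocol*

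**What the plan says.** **Safety windows.** Section 13.2 collects occurrences "from the first dose of IMP to 30 days after the last dose of IMP should be reported as adverse events". Section 13.3, under the reporting period for SAEs, says "Details of all SAEs will be documented from the commencement of treatment until 30 days post-treatment". The flowchart of assessments (Figure 1) agrees: its AE/SAE row is first marked at day 14, with nothing at screening or baseline.

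**Definition and relatedness.** Section 13.1 defines an AE as "any untoward medical occurrence in a patient or clinical trial subject administered a medicinal product". Under section 13.3 the clinician judges whether an SAE is related to the study drugs, and Appendix 6 speaks only of medication. Neither names a trial procedure.

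**Biopsies.** The baseline list in section 9 has "Core biopsy - if insufficient material left from diagnostic core biopsy". It adds that where the pathology consent was used before the diagnostic biopsy and enough cores were taken, "other additional biopsies will not be necessary at baseline". A frozen core is also listed at baseline, "only for sites participating in the frozen tissue sub-protocol". Section 16 gives the research purpose: "Additional core biopsies will be taken for formalin fixation to provide material for the TRANS NEO-EXCEL research tissue bank". The notes to Figure 1 place the baseline visit no more than 5 days ahead of the first dose. A second core biopsy follows at day 14.

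**The concern.** A trial normally accounts for harm from procedures that it adds for research as well as from its drugs. Here the same procedure, a core biopsy taken at least partly for research, is scheduled twice before surgery. The safety window covers the second occasion fully and the first only in part.

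The protocol recognises biopsy bleeding as a foreseeable issue in at least one group. Section 8.2 says "Because of possible interference with INR and also due to multiple biopsies being required, patients on warfarin are ineligible", and adds that excessive bleeding could disturb tumour measurement.

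At stake is whether the Study Office and the IDMC would learn of a bleed, infection or admission that followed a pre-treatment research biopsy. The event most worth knowing about is one serious enough to keep a randomised patient from starting treatment. As written, that event lies outside the window altogether.

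**Working it through.** The protocol states no figure on this point and no calculation applies. The check sets the timing of the biopsies against the reporting rules.

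**Inputs**
- AE window: first dose to 30 days after the last (13.2).
- SAE window: start of treatment to 30 days after it ends; later only if related and unexpected (13.3).
- Baseline visit: 0 to 5 days before the first dose (Figure 1 and its notes; the figure labels the visit Day 1).
- Baseline core: conditional on leftover diagnostic material. Frozen core: participating sites only (section 9).
- Pre-existing conditions: reportable only if they worsen or recur more often (exceptions in 13.2).

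**What happens to a biopsy complication under these rules**

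| Course of the event | Trial reporting route |
|---|---|
| Starts and settles between the baseline biopsy and the first dose | None: outside both windows, and outside the 13.1 definition because no trial drug has been given |
| Starts before the first dose, present and unchanged afterwards | None: counts as pre-existing |
| Starts before the first dose, worsens afterwards | Reported |
| Starts after the first dose | Reported, whatever the cause |
| Prevents a randomised patient from ever starting | None: there is no first dose, so the window never opens |
| Follows the day-14 biopsy | Reported |

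Three of the six courses have no route. All three concern the baseline biopsy, and nothing in the protocol gives a reason for treating the two occasions differently.

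**Other routes considered**
- Section 13.3 also asks investigators to report SAEs under local institutional policy. That is an additional, local route. It does not bring a pre-dose event to the Study Office.
- Section 10.3 has the reason for a clinician-initiated withdrawal recorded on the CRFs. This could leave a trace of a patient who never started, but it is not a safety report and carries no severity or relatedness assessment.

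**Length of the gap.** It is 0 to 5 days for biopsies at the baseline visit. It could be longer where research cores are taken during the diagnostic biopsy under early pathology consent, but that biopsy is being done for diagnosis anyway.

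**Number exposed.** Section 16 reads as if additional cores apply to all 1000 patients. Section 9 makes the separate baseline core conditional and restricts the frozen core to certain sites. The protocol does not say how many patients have a separate pre-treatment research biopsy, so 1000 is only a ceiling.

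**The case against.** The case against has several parts.

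**Harm from these biopsies does get reported.** A reader might infer that it never is. The protocol does not support that. Any event starting or worsening after the first dose is collected regardless of cause, and the gap is at most 5 days from the baseline visit. This stands, and it limits the point to the three courses identified above.

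**The scale is unknown.** A reader might apply assumed rates to the full sample: 1000 × 0.01 to 0.03 = 10 to 30 complications, and 1000 × 0.001 to 0.005 = 1 to 5 serious ones. The protocol gives no complication rate. The product also treats every patient as having a separate research biopsy and every complication as confined to the days before dosing. Section 9 contradicts the first step and the reporting rules contradict the second. These figures should not be used.

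**Attribution to celecoxib is protected.** A reader might think that day-14 complications are harder to interpret without a pre-dose counterpart. They are not: all arms have the day-14 biopsy, and the control is the concurrent randomised placebo group, 500 against 500. That group also gives some information on biopsy risk, though in patients taking an aromatase inhibitor. This objection stands in full.

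**The warfarin exclusion proves little.** It gives INR interference first and is a precaution for anticoagulated patients. It does not say that the biopsy is hazardous in those eligible. This stands.

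**The safety sections are consistent.** They all tie collection to drug exposure, so the protocol does not contradict itself. The biopsy consent and information sheets are not in the text at hand and the laboratory manuals are separate, so it cannot be said that such events are handled nowhere. This also stands. It does not alter the fact that the stated AE and SAE rules exclude these events.

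**Moving the window alone would not be enough.** The AE definition would still require an administered product. The annual reports to the MREC cover reactions judged related to trial medication, so a biopsy bleed would not enter them even inside the window. This is correct and shapes the remedy.

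**Conclusion.** The point holds in a limited form. Between a pre-treatment research biopsy and the first dose, the protocol's AE and SAE rules leave a gap. It affects complications that begin and resolve or stay stable in that interval, and those that prevent a randomised patient from starting treatment.

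The number of such events cannot be estimated from the protocol. It is probably small, because the baseline research biopsy is conditional or site-limited, the interval is short, and later onset or worsening is captured. The primary endpoint, the power and the randomised on-treatment safety comparison are untouched. This is an inexpensive improvement to safety reporting, with no bearing on the validity of the efficacy results.

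The conclusion assumes that no document outside the text at hand, such as the biopsy consent material or a laboratory manual, already opens trial safety reporting earlier.

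**What to change.** - **Sections 13.2 and 13.3:** start AE and SAE collection at the first trial-specific procedure (the pre-treatment research biopsy, where one is taken) or at the first dose, whichever is earlier. Leave the end of the window as it is. Make clear that a randomised patient who never starts treatment is covered.
- **Section 13.1:** extend the AE definition to occurrences that follow a trial procedure, so that a pre-dose event can qualify.
- **Section 13.3 and Appendix 6:** add trial procedures to the relatedness assessment, with one CRF item recording whether the event is related to a trial biopsy.
- **IDMC safety reports:** include these events, for both the pre-treatment and the day-14 biopsies.
- **Analysis:** keep the first dose as the start for treatment-emergent comparisons between arms, so that the randomised safety analysis does not change.

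The cost is short wording changes in section 13 and Appendix 6, one CRF item and a few more event forms.

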#### Reporting of SAEs to Regulatory Authorities

The CRCTU, Birmingham will report all fatal or life threatening SUSARs to the Medicines and Healthcare products Regulatory Agency (MHRA) and the Multi-Centre Ethics Committee (MREC) within 7 days of receiving initial notification from the study site. Any follow-up information will be provided within an additional 8 days. Non-fatal and non-life threatening SUSARs will be reported within 15 days. The CRCTU, Birmingham will submit an Annual Safety Report to the MHRA and MREC summarising all reported SARs.

The CRCTU, Birmingham will forward details of SUSARs to all Investigators in the form of an Annual Safety Report. SAEs will be reported to the relevant Pharmaceutical Companies as appropriate.

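### Protocol 13.3 is inconsistent for SAEs starting more than 30 days after the last dose: the site's own view of expectedness decides whether the Clinical Coordinator ever gets to assess it

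*Protocol*

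**What the plan says.** All the governing text is in section 13 of the protocol.

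- **Reporting period for SAEs (13.3).** Inside the window everything is captured: "Details of all SAEs will be documented from the commencement of treatment until 30 days post-treatment". After it, "SAEs occurring thereafter should be reported only if the Investigator believes them to be related and unexpected (i.e. SUSAR").
- **Documenting SAEs (13.3).** The site's task is stated as "The responsible clinician must determine the severity of an event" and the "relatedness of the events to the study drugs". The next sentence reads "Seriousness, relatedness, and expectedness will also be independently assessed by the Clinical Coordinator(s"). Either party can establish causality: "A SAE judged by the Investigator or Clinical Coordinator to have a reasonable causal relationship with the trial medication will be regarded as" a SAR.
- **Definition of a SUSAR (13.1).** A SAR is unexpected when "the nature, or severity of the event is not consistent with the applicable product information". The reference is therefore the product information, in nature or in severity.
- **Reporting of SAEs to Regulatory Authorities (13.3).** The 7-day period for fatal or life-threatening SUSARs runs from the site's first notification; other SUSARs have 15 days. The trials unit "will submit an Annual Safety Report to the MHRA and MREC summarising all reported SARs".

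Two other places bear on late events. Section 9, on follow-up after treatment, lists toxicity and survival among the items collected, about once a year for at least 5 years. Section 13.3 also asks investigators to report SAEs under their local institutional policy.

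**The concern.** Independent assessment by the Coordinator works as a check only if the event reaches the Coordinator. For late events, the reporting period rule makes the site's judgement on expectedness a condition of sending the form. The judgement that is meant to be checked thus decides whether any check takes place.

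What is at stake is the completeness of late safety reporting. If a site wrongly regards a late serious reaction as expected, nothing later in the trial's SAE route can correct it. A reaction that is rightly regarded as expected would belong in the annual report to the regulator and the ethics committee, which is not restricted to unexpected reactions. It will be absent because it was never reported.

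**Working it through.** No arithmetic decides this point. The check is to follow a late SAE through the stated rules.

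**Who assesses what under Documenting SAEs**

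- Responsible clinician: severity and relatedness. Expectedness is not listed.
- Clinical Coordinator: seriousness, relatedness and expectedness, independently.

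**What the site must decide under Reporting period for SAEs, after 30 days**

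- Relatedness and expectedness, both before a form is sent.

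**A new SAE starting more than 30 days after the last dose, by the Investigator's view**

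1. *Related and unexpected.* Reported. The Coordinator assesses it, the regulatory clock can start, and it enters the annual report.
2. *Related and expected, and the site is right.* No SAE form. The Coordinator does not see it. It is a SAR by definition, but not a reported one, so the annual summary omits it.
3. *Related and expected, and the site is wrong, so it is in truth a SUSAR.* No SAE form. The 7- or 15-day reporting does not start, because the trials unit has had no notification. The rule in section 13.5, that assessors assume celecoxib was given and the coordinating centre unblinds if the event is thought related, is not brought into play at coordinator level either.
4. *Unrelated.* No SAE form, so the Coordinator cannot overrule the site on causality. Relatedness is at least a judgement that Documenting SAEs gives to the clinician, so the mismatch over expectedness does not arise here.

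The inconsistency lies in cases 2 and 3.

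**Do other routes repair it?**

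- *Yearly follow-up (section 9).* Toxicity is listed, but with no stated assessment of seriousness, causality or expectedness and no 24-hour route. Sections 13.2 and 13.4 limit general AE recording to 30 days after the last dose, so what the item captures later is not clear.
- *Relapse/Death and long-term follow-up forms (section 10.2).* These would bring in a death and its cause, but not by the SAE route.
- *Local institutional policy (13.3).* This is additional to the trial route and is not said to reach the Study Office.
- *Follow-up of SAEs to recovery (13.4).* This covers following up SAEs, not how a new late one is reported.

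**How much time the narrower rule governs**

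- Treatment lasts 16 to 18 weeks: 16 × 7 = 112 days, 18 × 7 = 126 days.
- Adding 30 days, full SAE reporting covers about 142 to 156 days from the start of treatment. The narrower rule applies to the rest of a follow-up of at least 5 years.
- For the clinical trial authorisation, the study ends 30 days after the last patient's last dose (section 10.5). Any patient who stops at least one day before that last patient reaches day 31 while the trial is still open, so the gap exists during the trial.

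**The case against.** The strongest case on the other side is that this is a stated design choice. Limiting late reports to suspected unexpected reactions is an explicit rule, and an annual report on reported SARs is consistent with it, since it covers what is reported. The reporting period paragraph is itself part of 13.3 and expressly gives the Investigator the late judgement. The words also and independently in the Coordinator's sentence can be read as a second assessment following the site's own.

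Much of that stands. A reader might infer that 13.3 denies the Investigator any say on expectedness. It does not; two paragraphs of the same section sit badly together. A restriction on late reporting is also permissible in itself. What does not stand is the view that nothing needs reconciling: a second, independent assessment still needs a report to assess.

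Three other inferences are tempting, and the document does not support them.

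- *That such events are never reported anywhere.* Yearly follow-up, the death forms and local policy remain. What is lost is the trial SAE report and what depends on it.
- *That late cardiovascular or gastrointestinal events would be the ones left out, because section 3.5.2 discusses them.* Expectedness is judged against the product information, not the protocol's background text, and the product information is not in the document.
- *That the approximately 2.5-fold cardiovascular risk in section 3.5.2 measures the gap.* That figure comes from one trial of 400 to 800 mg daily, in a programme that treated patients for up to 4 years. It does not describe events that start more than 30 days after a 16- to 18-week course. The same section cites two other trials without an increased risk for celecoxib. Section 3.5.1 gives an effective half-life of about 11 hours, so 30 days is 720 / 11, or about 65 half-lives. Related late events may therefore be few.

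**Conclusion.** The point holds as an inconsistency within 13.3, limited to SAEs that start more than 30 days after the last dose and that the site considers related but expected. For these, the Coordinator's independent assessment cannot happen, a misclassified SUSAR does not reach expedited reporting, and the annual summary of SARs is incomplete.

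Its size cannot be stated. The protocol gives no late event rate, and the number could be close to zero. The primary endpoint, sample size and error rates are untouched, so a reader should not infer any effect on the efficacy conclusions. The conclusion assumes that the reporting period rule is applied as written, and that the toxicity item at follow-up carries no causality or expectedness assessment beyond what section 9 states. It is a cheap improvement to safety reporting, not a flaw that threatens the trial.

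**What to change.** Amend Reporting period for SAEs in 13.3 so that, after 30 days, an SAE is reported if the Investigator believes it related to trial medication, whether or not it is expected. State that the Clinical Coordinator then assesses expectedness against the product information, as under Documenting SAEs, and that these events are included in the Annual Safety Report.

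This removes the site's expectedness judgement as a gate and brings the two paragraphs into line. It does not change the handling of late events that the site considers unrelated. The cost is one sentence in the protocol and a few additional SAE forms on the existing form and route. No treatment rule changes.
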